Brief Title: GER Poses a Potential Risk for Late Complications of BPD

Official Title: Gastroesophageal Reflux Really Pose a Potential Risk for Late Complications of Bronchopulmonary Dysplasia in Extremely Premature Infants

Identifiers: NCT03014453

Unique Protocol ID: A333-1

Sponsor: Shengjing Hospital

Investigator: [name]

Official Title: Professor

Affiliation: Shengjing Hospital

Study Start: July 1, 2017

Document Date: March 24, 2020

Study Protocol

Research background

Bronchopulmonary dysplasia (BPD) is a common condition in the low birth weight infants. Although most of the BPD symptoms improved after a regular treatment in infancy, there are still a few late complications left such as the frequent respiratory symptoms, a slower weight gain and even sudden death. These late complications have made so much trouble to the healthcare of BPD infants. How to find the risk factors and to reduce the prevalence of these late symptoms becomes necessary. In this study, a cohort of BPD infants was observed with the late complications obtained by a monthly followed up for 18 months after discharge, the prevalence and risk factors were analyzed via logistic regression, calculating odd ratios (OR) and 95% confidence intervals. As one of the risk factors, GER was verified whether to play a critical role in these late complications.

Research purposes

A prospective cohort study is carried out to explore the potential risk of gastroesophageal reflux as a late complication of bronchopulmonary dysplasia in preterm infants.

Methods

Patients

The study was approved by the Ethics Committee of China Medical University. Written consent was obtained from the parents. The cohort included infants born at or before 32 weeks gestational age (GA) with BPD between January 2017 and July 2018 at Shengjing Hospital of China Medical University, the First Hospital of Jilin University, and Shanghai General Hospital of Shanghai Jiao Tong University. BPD was diagnosed at 36 weeks postmenstrual age (PMA) on the National Heart, Lung and Blood Institute classification and categorized as “mild, moderate or severe”. Infants with no BPD, severe gastrointestinal malformations and refused GER monitoring were excluded.

Detailed information on the BPD infants, including age, sex, Apgar scores, treatments after

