born, clinical symptoms, and other clinical information we designed. After discharge, all the patients received a regular follow up for late complications including respiratory symptoms (including home respiratory support, respiratory medication administration, cough without cold at least once per week, re-hospitalization due to respiratory diseases), vomiting when feeding, hypoxic ischemic injury, retinopathy of prematurity, rehospitalization and sudden death.

Measurements and definitions

Respiratory morbidity included pneumonia, respiratory medication administration for dyspnea, cyanosis and intermittent apnea, and cough without cold at least once per week. Vomiting when feeding referred to vomiting at least once a week and retinopathy of prematurity were diagnosed by local doctors. The diagnoses of hypoxic-ischemic injury mainly depend on MRI.

pH-MII methods

A 24h pH-MII measurement was carried out twice in each infant in the study group of 116 infants with BPD. The first test was performed at 36 weeks PMA and the second, at the last interview between the 17th and 18th month of PMA. Pathological GER was diagnosed when both the tests were positive for GER. In pH-MII monitoring, the probe (Kanglian, Beijing, China) had eight impedance channels (Z1-Z6) and two pH channels. The probe was inserted transnasally into the esophagus. The proximal pH channel was positioned 3 cm above the left diaphragm and the distal pH channel was positioned in the stomach. The position of the pH channels was verified by chest radiography. The data were evaluated using the manufacturer's software and each trace was manually reviewed by the same operator. This operator was not informed of the final outcome.

GER was diagnosed based on the proximal pH channel. Reflux index (RI), which is the percentage of the total recording time with an esophageal pH < 4, was used to categorize pathological GER. Acid GER was defined by a RI > 12, irrespective of the impedance value. Weak acid reflux was defined as a pH between 4–7 when the impedance value decreased > 20% from the baseline while the duration of intragastric pH > 4 for < 70% of the time. DGER was diagnosed for RI < 12 with decreasing impedance and when the intragastric pH > 4 for > 70% of the time. GER without acid GER and DGER was regarded as non GER.

Determination of gastric sodium ions

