The gastric juice was sampled from 89 infants. All medications were forbidden 24 hours prior to sample collection. A feeding tube was always placed for daily meals. Gastric juice was taken for 30 minutes via the feeding tube before meal at 2AM, 10AM and 6PM in a given day with an interval of 8 hours, and was analyzed on a rapid ion analyzer (BHF-II, Bairikang, Beijing). Each patient was sampled three times and a Na⁺ concentration > 50 mmol/L in all three samples was considered positive.

Statistics

Continuous variables were graded as categorical variables and the categorical variables were expressed as frequency and percentage. Chi-square test was used to compare categorical differences. Adjusted odds ratios (ORs) and corresponding 95% confidence intervals (CIs) for every late complication of BPD were estimated separately with multiple logistic regression models (forward). Potential confounders included gender, GA (< 30 weeks and \geq 30 weeks), birth weight (< 1500 g and > 1500 g), Apgar score, invasive ventilation (< 7 days and \geq 7 days), pulmonary surfactant, caffeine, ventilator-associated pneumonia, and GER were

adjusted. All computations relied on standard software (SPSS v19.0; SPSS Inc, Chicago, IL, USA), and statistical significance was set at $P < 0.05$.

Results

Prevalence of Late Complications

Among the 116 infants with BPD in the final cohort, late complications occurred in 74 infants with an overall prevalence of 63.79%. These complications included respiratory symptoms in 49.14% (n=57) infants, including pneumonia (n=10, 8.62%); dyspnea, cyanosis and intermittent apnea warranting respiratory medication administration (n=25, 21.55%), and cough (n=44, 37.93%). Vomiting occurred in 45 (38.79%), ROP in 30 (25.86%), and hypoxic-ischemic injury in 4 (3.45%) infants. One (0.86%) infant suffered sudden infant death syndrome. Re-hospitalization was recorded in 31 (26.72%) infants.

GER Prevalence in BPD

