Pathological GER occurred in 49 infants with BPD with an overall prevalence of 42.24%, including acid GER (n=21, 18.10%) and DGER (n=28, 24.14%). SI, SSI, and SAP measurements were $> 99\%$ in all 49 infants, confirming the association between reflux events and symptoms. Weak acid GER was found in almost all infants including those with acid GER, DGER and non GER. The percentage of weak acid GER events over the overall reflux episodes varied from 40.74–100%, and there was no significant difference among infants with acid GER, DGER and non GER. In the evaluation of DGER, 33 infants are positive for pH-MII monitoring, and gastric $\text{Na}^+ > 50$ mmol/L was noted in 28 infants who were finally diagnosed as DGER. Five infants positive for pH-MII and negative for gastric $\text{Na}^+ > 50$ mmol/L were diagnosed as weak acid GER. No infants negative for pH-MII and positive for

gastric $\text{Na}^+ > 50 \text{ mmol/L}$ were noted. Among the BPD infants, the prevalence of acid GER and DGER was 12% and 17.33% in mild BPD, 32.14% and 32.14% in moderate BPD, and 23.08% and 46.15% in severe BPD individually. Among the 74 symptomatic infants, the prevalence was 14.66% and 21.55%.

Risk Factors for Late Complications

Accordingly, risk factors for respiratory symptoms were $\text{GA} \leq 30$ weeks (odds ratio, OR=3.213; 95% CI, 1.221-8.460), birth weight $< 1500 \text{ g}$ (OR=2.803; 95% CI, 1.014-7.749), invasive ventilation > 7 days (OR=4.952; 95% CI, 1.508-16.267), acid GER (OR=4.630; 95% CI, 1.305-16.420), and DGER (OR=5.588; 95% CI, 1.770-17.648). Risk factors for vomiting were $\text{GA} \leq 30$ weeks (OR=5.813; 95% CI, 2.424-13.940), acid GER (OR=3.394; 95% CI, 1.107-10.403), and DGER (OR=4.379; 95% CI, 1.552-12.354). Risk factors for ROP were $\text{GA} \leq 30$ weeks (OR=8.741; 95% CI, 3.203-23.851), while the major risk factors for re-hospitalization were $\text{GA} \leq 30$ weeks (OR=3.894; 95% CI, 1.405-10.791), acid GER (OR=5.866; 95% CI, 1.640-20.972), and DGER (OR=8.436; 95% CI, 2.697-26.382).

Conclusion

In summary, the prevalence of late complications of BPD is high; pediatricians should pay great attention to BPD infants after discharge to reduce the damage caused by these late complications. GER, or rather DGER, is a potential risk for the late complications of BPD.

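### BPD severity is strongly tied to GER in the reported figures but is not among the listed covariates, so confounding of the GER odds ratios is possible and no reported result tests it

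*Combined protocol and SAP*

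**What the plan says.** Under Methods, Patients: "BPD was diagnosed at 36 weeks postmenstrual age (PMA) on the National Heart, Lung and Blood Institute classification", with three grades (mild, moderate, severe). Under pH-MII methods, for GER: "The first test was performed at 36 weeks PMA".

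Under Statistics, the odds ratios for each late complication "were estimated separately with multiple logistic regression models (forward"). The potential confounders are gender, gestational age, birth weight, Apgar score and invasive ventilation, and the list closes with "pulmonary surfactant, caffeine, ventilator-associated pneumonia, and GER were" adjusted. Severity is not named.

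Under GER Prevalence in BPD, GER is broken down by severity: "the prevalence of acid GER and DGER was 12% and 17.33% in mild BPD, 32.14% and 32.14% in moderate BPD". For the severe grade the corresponding figures are 23.08% (acid GER) and 46.15% (DGER). No complication is broken down by severity, and Risk Factors for Late Complications reports no severity term, stratified result or sensitivity analysis. The Conclusion presents GER, and DGER in particular, as a possible risk for late complications.

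**The concern.** The study asks whether GER itself adds risk among infants who all have BPD. Severity of BPD is the obvious rival explanation: it is a grade of the disease whose late complications are the outcome, it was recorded, and it is unevenly spread across the GER groups. If severity also raises the risk of these complications beyond what the listed covariates capture, part of each GER odds ratio belongs to severity. A reader cannot tell how much.

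The listed covariates may stand in for severity in part, but the documents do not show that they do. Selection was forward. The risk factors reported for vomiting, and the major ones for re-hospitalization, are only gestational age and the two GER terms. Invasive ventilation and birth weight appear only for respiratory symptoms.

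Two lower limits lie close to 1, so a modest shift would matter there: vomiting, "acid GER (OR=3.394; 95% CI, 1.107-10.403"), and acid GER for respiratory symptoms (lower limit 1.305).

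**Working it through.** **1. Recover the severity-by-GER table.** Inputs: the six percentages by severity, 116 infants, 21 with acid GER and 28 with DGER. A search over all whole-number group sizes that sum to 116 finds one solution, and it returns the stated totals.

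| | Acid GER | DGER | Non-GER | Total |
|---|---|---|---|---|
| Mild | 9 | 13 | 53 | 75 |
| Moderate | 9 | 9 | 10 | 28 |
| Severe | 3 | 6 | 4 | 13 |
| Total | 21 | 28 | 67 | 116 |

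**2. Strength of the severity-GER link.**
- Any GER: 22/75 (29.3%), 18/28 (64.3%), 9/13 (69.2%). Expected counts are 31.68, 11.83 and 5.49. Chi-square = 5.12 + 5.58 + 3.88 = 14.58 on 2 df, p=0.0007.
- Moderate/severe versus mild, any GER: OR = (27 × 53)/(22 × 14) = 4.65. SE of the log OR = √(1/22 + 1/53 + 1/27 + 1/14) = 0.416, so the 95% CI is 2.06-10.49.
- Acid GER versus non-GER: (12 × 53)/(9 × 14) = 5.05 (1.77-14.36).
- DGER versus non-GER: (15 × 53)/(13 × 14) = 4.37 (1.69-11.27).
- Share with moderate/severe BPD: acid GER 12/21 (57%), DGER 15/28 (54%), non-GER 14/67 (21%). The imbalance is about equal for the two GER types.

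**3. A simple illustration.** Take vomiting (45 events), an assumed severity OR of 2 (moderate/severe versus mild) and no GER effect. Solving 75p₀ + 41p₁ = 45 with odds ratio 2 gives p₀ = 0.329 and p₁ = 0.495. The risk is then (9 × 0.329 + 12 × 0.495)/21 = 0.424 with acid GER and (53 × 0.329 + 14 × 0.495)/67 = 0.364 without GER. That is a spurious OR of 1.29. Dividing it out takes 3.394 to 2.64 and the lower limit 1.107 to 0.86.

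**4. Fuller scenarios.** For each assumed severity OR, solve for the acid GER and DGER odds ratios that return the reported ones when severity is omitted, keeping the event totals (57 respiratory, 45 vomiting, 31 re-hospitalization). Then:

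lower limit = adjusted OR × exp(−1.96 × SE from reported CI × SE ratio with versus without severity).

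- A: mild versus moderate/severe, OR 2 to 3, crude imbalance.
- B: as A, with half of the log-OR imbalance already absorbed by the listed covariates (severity-GER ORs of 2.25 for acid GER and 2.09 for DGER).
- C: OR 2 to 3 per grade, crude imbalance. Severe versus mild is then 4 to 9.

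Reported OR divided by adjusted OR: A 1.21-1.41, B 1.08-1.14, C 1.28-1.47.

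Example (A, OR 2, acid GER and vomiting): the adjusted OR is 2.70. SE = ln(10.403/1.107)/3.92 = 0.572 and the SE ratio is 1.044. Lower limit = 2.70 × exp(−1.96 × 0.572 × 1.044) = 0.84.

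| Association | Reported OR (95% CI) | Lower limit over A-C |
|---|---|---|
| Acid GER, vomiting | 3.394 (1.107-10.403) | 0.69-0.98 |
| Acid GER, respiratory | 4.630 (1.305-16.420) | 0.86-1.17 |
| Acid GER, re-hospitalization | 5.866 (1.640-20.972) | 1.07-1.46 |
| DGER, vomiting | 4.379 (1.552-12.354) | 0.99-1.41 |
| DGER, respiratory | 5.588 (1.770-17.648) | 1.20-1.62 |
| DGER, re-hospitalization | 8.436 (2.697-26.382) | 1.80-2.47 |

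The low end of each range comes from C at OR 3, the high end from B at OR 2. The lowest adjusted OR is 2.3 (acid GER and vomiting, C).

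**The case against.** The strongest reply is that no confounding has been shown. It needs a link between severity and outcome beyond the adjusted covariates, and the documents give none. If that residual OR is 1, nothing changes. This stands, and it is why the point claims only that confounding is possible.

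A second reply is that the illustration treats covariate-adjusted odds ratios as crude, applies one severity effect to every outcome, and takes its extremes from scenario C. Invasive ventilation, a marker of respiratory burden, was a candidate yet is not reported as a risk factor for vomiting, the most fragile result. This stands in part: the scenarios without absorption probably overstate the shift. Under B, acid GER and respiratory symptoms keep a lower limit of 1.13-1.17, and only acid GER and vomiting falls below 1 (0.93-0.98). But forward selection can drop real effects, so ventilation's absence from a model is weak evidence about severity.

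Third, severity and the first GER test share the 36-week time point, and the documents do not say which comes first. Adjustment may therefore remove some genuine GER effect. This also stands; showing the odds ratios both with and without severity avoids having to choose.

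Finally, the confounder list is introduced as what was included, so severity may have been examined and not reported. For the reader the gap is the same.

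**Conclusion.** The concern holds. Severity was graded, is strongly related to both GER types (ORs of about 4 to 5) and appears in neither the covariate list nor any reported model. Whether this biases the GER odds ratios cannot be settled from the documents.

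Under an assumed residual severity OR of 2 to 3, the associations weaken but all six odds ratios stay above 1. Acid GER and vomiting loses its lower limit above 1 in every scenario. Acid GER and respiratory symptoms may lose it, and DGER and vomiting touches 0.99 only at the extreme. The other three keep it throughout. Acid GER looks more fragile because its reported limits start nearer 1, not because it is more confounded. The severity ORs and the halving in B are assumptions, so these are ranges and not bounds.

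This should be fixed but does not overturn the study: the Conclusion is already cautious, and what is missing is the severity-adjusted result beside it. Confidence is medium.

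**What to change.** Add under Statistics:

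> Post-hoc sensitivity analysis. For respiratory symptoms, vomiting and re-hospitalization, GER (non-GER, acid GER, DGER) and BPD severity (mild versus moderate/severe) are both forced into the logistic model with the other terms of the reported model, without forward selection. The acid GER and DGER odds ratios (95% CI) are shown with and without severity.

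Keep the other terms identical in both models, so that only severity differs. State in the Conclusion which associations change materially, note the shared 36-week time point and possible over-adjustment, and do not discard an association only because it loses P<0.05.

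Tabulate each outcome by severity grade, and by severity within GER group. Severity alone is not enough. The text says "Among the 74 symptomatic infants, the prevalence was 14.66% and 21.55" per cent, but those percentages match whole infants only out of 116 (17 and 25), not out of 74. Any late complication then occurred in 17/21 acid GER, 25/28 DGER and (74 − 42)/67 = 32/67 non-GER infants. Even if severity had no effect of its own, the expected rates would be (9 × 17/21 + 13 × 25/28 + 53 × 32/67)/75 = 59% in mild and (12 × 17/21 + 15 × 25/28 + 14 × 32/67)/41 = 73% in moderate/severe BPD. Cells within GER group will be small, since only 13 infants have severe BPD.

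Cost: a re-run on existing data, one table, one paragraph and one degree of freedom per model. The SE of the GER log odds ratios rises by about 3-6% in scenario A, 1-4% in B and 3-8% in C. Counting the reported terms, events per term fall from 31/3 = 10.3 to 31/4 = 7.8 for re-hospitalization, 57/5 = 11.4 to 57/6 = 9.5 for respiratory symptoms, and 45/3 = 15.0 to 45/4 = 11.3 for vomiting. Only the major risk factors are listed for re-hospitalization, so that model may hold more terms. Against the full candidate list (at least 10 terms, with GER as two), re-hospitalization already has 31/10 = 3.1 events per term, and 31/11 = 2.8 with severity. That is the reason to force a small fixed set and not repeat the selection.

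### The written DGER rule (pH-MII alone, 33 infants) is not the rule analysed (pH-MII plus gastric sodium, 28 infants), and the Conclusion ranks DGER above acid GER without comparing them

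*Combined protocol and SAP*

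**What the plan says.** **Methods, pH-MII methods.** DGER has a definition with no sodium term: "DGER was diagnosed for RI < 12 with decreasing impedance and when the intragastric pH > 4 for > 70% of the time". Weak acid reflux carries the opposite intragastric condition: "while the duration of intragastric pH > 4 for < 70% of the time". Two further rules apply: "Pathological GER was diagnosed when both the tests were positive for GER", and "GER without acid GER and DGER was regarded as non GER".

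**Methods, Determination of gastric sodium ions.** Gastric juice was taken from 89 infants, and a positive result needs more than 50 mmol/L in all three samples. The section does not say that this result enters the DGER diagnosis.

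**Statistics.** Adjusted odds ratios for each complication "were estimated separately with multiple logistic regression models (forward" selection). GER is among the listed covariates. Its reference category is not named.

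**Results, GER Prevalence in BPD.** "In the evaluation of DGER, 33 infants are positive for pH-MII monitoring". Of these, 28 were also sodium-positive and received the final DGER diagnosis. The five who were sodium-negative "were diagnosed as weak acid GER".

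**Results, Risk Factors, and Conclusion.** Acid GER and DGER each have an odds ratio for respiratory symptoms, vomiting and re-hospitalization. The Conclusion then narrows its statement on risk from GER to DGER.

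**The concern.** There are two linked problems.

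First, the exposure that was analysed is not the one that Methods defines. Sodium acts as a second gate that the written rule does not contain. The five infants it removes are given a label whose written criterion they appear to contradict: pH-MII positivity for DGER needs intragastric pH above 4 for more than 70% of the time, and weak acid reflux needs less than 70%. Since anything other than acid GER or DGER is non GER, these five probably sit in the comparison group of every model. An analyst working from Methods would therefore build a different exposure variable and a different reference group.

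Second, the Conclusion prefers DGER to GER in general. That is a comparison between reflux types, and the analysis compares each type only with the reference. A larger point estimate for DGER in three models does not amount to three independent confirmations, because the infants and the reference group are the same each time.

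**Working it through.** **1. Reproduce the reported counts.** Of 116 infants: acid GER 21/116 = 18.10%, DGER 28/116 = 24.14%, pathological GER 49/116 = 42.24%. All match. The acid GER and DGER percentages by BPD severity fit only one split of 116, namely 75 mild, 28 moderate and 13 severe. This gives acid GER 9 + 9 + 3 = 21 and DGER 13 + 9 + 6 = 28. So 28 is the count carried through the prevalence results. That the regressions also used 28 is an inference, because no model table is given.

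**2. Counts under the written rule.** If all five discordant infants were positive on both pH-MII tests (an assumption), DGER is 33/116 = 28.4%, pathological GER is 54/116 = 46.6%, and non GER falls from 116 − 49 = 67 to 116 − 54 = 62.

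**3. DGER against acid GER, from the printed intervals.** SE(log OR) = ln(upper/lower)/(2 × 1.96). The log ratio of ORs is ln(OR DGER/OR acid), with SE = √(SE_acid² + SE_DGER² − 2·cov). The covariance is not reported. A shared reference group makes it positive, so it was set to 0 and to 0.15 (a correlation of about 0.40 to 0.50).

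| Outcome | OR acid (SE) | OR DGER (SE) | Ratio | 95% CI, cov 0 | 95% CI, cov 0.15 | p (cov 0; 0.15) |
|---|---|---|---|---|---|---|
| Respiratory | 4.630 (0.646) | 5.588 (0.587) | 1.21 | 0.22–6.68 | 0.32–4.57 | 0.83; 0.78 |
| Vomiting | 3.394 (0.572) | 4.379 (0.529) | 1.29 | 0.28–5.94 | 0.44–3.82 | 0.74; 0.64 |
| Re-hospitalization | 5.866 (0.650) | 8.436 (0.582) | 1.44 | 0.26–7.95 | 0.38–5.44 | 0.68; 0.59 |

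For re-hospitalization at covariance 0: SE = √(0.650² + 0.582²) = 0.872, ln(8.436/5.866) = 0.363, and exp(0.363 ± 1.96 × 0.872) = 0.26 to 7.95. For p < 0.05 the correlation between the two log ORs would have to be about 0.99, 0.98 and 0.96 for the three outcomes in turn.

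**4. How much five infants could matter (illustration only).** The five infants' outcomes are not reported, so the adjusted ORs cannot be recomputed. A crude table for any late complication, which the document does not model, can be back-solved. Results says "Among the 74 symptomatic infants, the prevalence was 14.66% and 21.55" per cent. These do not fit a denominator of 74 (11/74 = 14.86%, 16/74 = 21.62%), but 17/116 = 14.66% and 25/116 = 21.55% match exactly. This gives 17/21 symptomatic with acid GER, 25/28 with DGER, and (74 − 17 − 25)/67 = 32/67 with non GER.

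- As coded: (25/3)/(32/35) = 9.1.
- Five moved to DGER, k of them symptomatic: [(25 + k)/(8 − k)]/[(32 − k)/(30 + k)] runs from 2.9 (k = 0, 95% CI from 1.15) to 13.0 (k = 5).
- Five excluded: (25/3)/[(32 − k)/(30 + k)] runs from 7.8 to 10.8.

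The DGER association stays above 1 throughout. The order of DGER and acid GER does not always hold: acid GER odds are 17/4 = 4.25, against DGER odds of 25/8 = 3.1 (k = 0), 26/7 = 3.7 (k = 1) and 27/6 = 4.5 (k = 2). If the five were a random draw from the 67, the hypergeometric probability of k = 0 or 1 is 0.207.

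**The case against.** The strongest reply is that nothing is hidden. Methods describes the sodium test and its threshold, and Results states how 33 became 28, so a reader of the whole document can reconstruct the analysed group. That is true, and it makes this a gap between two stated rules rather than a concealed change. It does not reconcile the rules, nor does it explain how infants above the 70% limit come to carry a label that requires them to be below it.

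It can also be said that the document does not state whether the 33 were positive once or on both tests, so 33 and 54 may not be the exact written-rule counts, and that the reference group is inferred. Both points stand, and the figures above are conditional on them. Because Results attributes the relabelling to sodium, the inconsistency itself probably survives.

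The crude illustration rests on back-solved counts and an unmodelled outcome. The random-draw probability is weak, since these five were selected for a DGER-type trace. That part should carry little weight, and the conclusion does not depend on it.

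Finally, the Conclusion speaks only of a potential risk, DGER has the larger estimate in all three models, and the contrast is too imprecise to settle the order. That imprecision is a reason not to rank the two.

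**Conclusion.** Both parts hold. The definition of DGER in Methods and the one applied in Results differ by five of 33 infants, and the five are placed in a category whose written criterion they appear not to meet. Under the written rule, DGER prevalence would be up to 28.4% instead of 24.1%, and pathological GER up to 46.6% instead of 42.2%, if all five were positive on both tests. That they sit in the regression reference group is likely but not stated.

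The reported odds ratios support DGER as a risk factor against non GER, and that is not challenged. They do not support placing it above acid GER: the ratios are 1.21 to 1.44, with p between 0.59 and 0.83 over the covariances assumed, and only a correlation of at least 0.96 between the two log ORs would bring any of them to p < 0.05. The mismatch and the wording should be corrected; the main association does not fall with them.

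**What to change.** 1. Reconcile the DGER and weak acid definitions in Methods and Results into one stated analysis rule. Say whether both pH-MII tests must meet it and, if sodium is part of it, how the 116 − 89 = 27 infants without a gastric sample are classified.
2. Name the reference group for the GER terms in each regression.
3. Refit each model under the alternative rule: 33 as DGER if 28 is primary, or the reverse. If 28 is primary, add a sensitivity analysis without the five discordant infants.
4. Add a one-degree-of-freedom DGER-versus-acid GER contrast, with its 95% CI, to the models for respiratory symptoms, vomiting and re-hospitalization.
5. Unless that contrast supports DGER, have the Conclusion refer to pathological GER, both acid GER and DGER, in place of the emphasis on DGER alone.

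The cost is a few sentences in Methods and the Conclusion and a re-run with five infants recoded or excluded. No new data are needed. The price is a weaker DGER-specific message.
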